4.0 OBJECTIVES

4.1 Primary objective

The primary objective of the single arm phase II trial is to determine whether the surgery feasibility rate of neoadjuvant pembrolizumab is not significantly worse than the historical surgical feasibility rate of neoadjuvant chemotherapy. Surgery feasibility rate of a neoadjuvant therapy is the percent of

20

The information contained in this document is regarded as confidential, and may not be disclosed to another party unless such disclosure is required to initiate the study, to conduct study-related activities, or to comply with national, state, or local laws and regulations. Written authorization from the coordinating site and sponsor is required for disclosure otherwise.

11 Nov 2018

patients who are able to undertake surgery after the neoadjuvant therapy. A total of 30 eligible patients will be registered to the single arm trial. Taking 5% rate of cancellation and ineligibility into account, the trial will enroll a total of 32 patients and eligible subjects (not screen failures) will be followed for 2 years for both disease recurrence and death.

Primary Objective Sample Size Justification

According to Pisters et al (JCO 2010), approximately 80% of subjects undergo surgical exploration within 42 days of day 1 of the last cycle of standard neoadjuvant chemotherapy. We would like to test the following hypotheses:

$$H_0: p \geq 0.80 \text{ vs. } H_a: p < 0.65$$

where p is the true surgery feasibility rates after neoadjuvant pembrolizumab. With 30 evaluable patients receiving protocol treatment, the study has approximately 84.6% power rejecting $H_0: p \geq 0.80$ when $p=0.65$ at one-sided significance level of 15%.

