9.5 Surgery

Surgery to occur at 4-8 weeks (days 29-56) or subject will be removed from trial unless approved by PI. If pembrolizumab dose 2 is delayed, then there should be at least 2 days between pembrolizumab infusion and surgery.

The ability to perform surgery will be assessed by the surgeon and will be based on physical exam and radiological evaluation. Surgical therapy will be individualized based on the surgical judgment and patient preference and is not dictated by study protocol. Excess tumor tissue samples will also be collected at time of surgical resection after determination that adequate tumor has been taken by surgical pathology for all standard clinical studies. Specific instructions for processing and shipping are provided in Appendices G & H.

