11.3.2 Selection and Timing of Doses

Patients in this study will receive neoadjuvant pembrolizumab on Days 1 and 22, and adjuvant pembrolizumab every 21 days for 4 cycles after completion of all standard therapy.

Trial treatment should be administered on Day 1 of each cycle after all procedures/assessments have been completed as detailed on the Trial Flow Chart (Appendix A). Trial treatment may be administered up to 3 days before or after the scheduled Day 1 of each cycle due to administrative reasons.

All trial treatments will be administered on an outpatient basis. Pembrolizumab 200 mg will be administered as a 30-minute IV infusion every 3 weeks. Sites should make every effort to target infusion timing to be as close to 30 minutes as possible. However, given the variability of infusion pumps from site to site, a window of -5 minutes and +10 minutes is permitted (i.e., infusion time is 30 minutes: -5 min/+10 min).

The Pharmacy Manual contains specific instructions for the preparation of the pembrolizumab infusion fluid and administration of infusion solution.

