11.4 Pembrolizumab Dose Modifications

Adverse events (both non-serious and serious) associated with pembrolizumab exposure may represent an immunologic etiology. These adverse events may occur shortly after the first dose or several months after the last dose of treatment. Pembrolizumab must be withheld for drug-related toxicities and severe or life-threatening AEs as per Table 1 below.

If pembrolizumab is delayed more than two weeks due to a related AE, then pembrolizumab will be discontinued and patients should proceed to surgical resection when clinically appropriate.

Table 1
Dose Modification Guidelines for Drug-Related Adverse Events

Toxicity	Hold Treatment For Grade	Timing for Restarting Treatment	Treatment Discontinuation
Diarrhea/Colitis	2-3	Toxicity resolves to Grade 0-1.	Toxicity does not resolve within 12 weeks of last dose or inability to reduce corticosteroid to 10 mg or less of prednisone or equivalent per day within 12 weeks.
	4	Permanently discontinue	Permanently discontinue
AST, ALT, or Increased Bilirubin	2	Toxicity resolves to Grade 0-1	Toxicity does not resolve within 12 weeks of last dose.
	3-4	Permanently discontinue (see exception below)	Permanently discontinue
Type 1 diabetes mellitus (if new onset) or Hyperglycemia	T1DM or 3-4	Hold pembrolizumab for new onset Type 1 diabetes mellitus or Grade 3-4 hyperglycemia associated with evidence of beta cell failure.	Resume pembrolizumab when patients are clinically and metabolically stable.
Hypophysitis	2-4	Toxicity resolves to Grade 0-1 Therapy with Pembrolizumab can be continued while endocrine replacement therapy is instituted	Toxicity does not resolve within 12 weeks of last dose or inability to reduce corticosteroid to 10 mg or less of prednisone or equivalent per day within 12 weeks.
	4		
Hyperthyroidism	3	Toxicity resolves to Grade 0-1	Toxicity does not resolve within 12 weeks of last dose or inability to reduce corticosteroid to 10 mg or less of prednisone or equivalent per day within 12 weeks.
	4	Permanently discontinue	Permanently discontinue
Hypothyroidism	2-4	Therapy with pembrolizumab can be continued while thyroid	Therapy with pembrolizumab can be continued while thyroid

Toxicity	Hold Treatment For Grade	Timing for Restarting Treatment	Treatment Discontinuation
		replacement therapy is instituted	replacement therapy is instituted.
Infusion Reaction	3-4	Permanently discontinue	Permanently discontinue

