27.0 STATISTICAL METHODS AND ANALYTICAL PLANS

27.1 Statistical Considerations

Sample size justification

Futility Analysis

Futility analysis is often used for assessing clinical efficacy before the trial reaches target accrual and stops the trial early if the therapy clearly performs worse than control. The primary objective of this one-arm phase II trial is not to evaluate the efficacy of pembrolizumab in this population. Since it is unlikely that the therapy will harm the patients, a futility analysis on the percentage of patients with adequate TIL collection is unnecessary.

Evaluation of Investigational Therapy Safety and Feasibility

Analytic methods

Overview

The primary objective of the single arm phase II trial is to determine whether the surgery feasibility rate of neoadjuvant pembrolizumab is not significantly worse than the historical surgical feasibility rate of neoadjuvant chemotherapy. Surgery feasibility rate of a neoadjuvant therapy is the percent of patients who are able to undertake surgery after the neoadjuvant therapy. A total of 30 evaluable patients will be entered to the single arm trial. Taking 15% rate of cancellation and ineligibility into account, the trial will enroll a total of 35 patients and eligible subjects (not screen failures) will be followed for 2 years for both disease recurrence and death. Following that, patients will be followed every 6 months for up to five years.

Primary Objective Sample Size Justification

According to Pisters et al (JCO 2010), approximately 80% of subjects undergo surgical exploration within 42 days of day 1 of the last cycle of standard neoadjuvant chemotherapy. We would like to test the following hypotheses:

$$H_0: p \geq 0.80 \text{ vs. } H_a: p \leq 0.65$$

where p is the true surgery feasibility rates after combined neoadjuvant chemotherapy and pembrolizumab. With 30 evaluable patients receiving protocol treatment, the study has approximately 84.6% power rejecting $H_0: p \geq 0.80$ when $p = 0.65$ at one-sided significance level of 15%.

Adverse event monitoring: In this trial design it is difficult to accurately attribute adverse events to pembrolizumab, surgery, or other causes. Further, the analysis of treatment toxicities as isolated events will not best represent whether or not the combination of pembrolizumab followed by surgery is safe and feasible. Therefore, this safety and feasibility trial will be evaluated by the following criteria:

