- 1) Whether the cumulative percentage of deaths among all treated patients related to any of the study treatments from the first pembrolizumab treatment until 30 days after surgery exceeds 17%.
- 2) If the cumulative percentage of all treated patients deemed unable to go to surgery due to adverse events attributed to neoadjuvant therapy exceeds 20%. The percentage of patients unable to go to surgery after pembrolizumab is a conservative estimate based on data reported for a SWOG trial that studied neoadjuvant chemotherapy in early stage lung cancer (22).

The first 10 treated patients will be evaluated for safety and feasibility. If in the first ten patients the criteria for overall therapy being not safe or feasible is met, accrual to the study will be suspended to allow for investigation. After consideration by the study team and the IRB, a decision will be made as to whether accrual can be resumed, potentially with modifications to entry criteria and/or study conduct. In addition, all toxicity patterns will be monitored by the DCI Safety Oversight Committee.

The trial will be stopped for accrual whenever a total of 35 patients are registered or at least one of the thresholds of the safety and feasibility criteria is exceeded. In the event either of these two thresholds is exceeded, the investigational therapy will be considered “infeasible” in this setting.

Accrual and follow-up

With an expected rate of 2 patients being enrolled each month, the trial will take about 16 months to reach the target accrual. All registered patients will be followed for tumor response, disease free survival and overall survival.

Statistical Analysis Plan

Surgery feasibility rate, the primary endpoint of the trial, will be analyzed using the data from all evaluable patients, who are defined as the patients who meet eligibility criteria and has received at least 1 dose of pembrolizumab. The surgery feasibility rate of neoadjuvant pembrolizumab as well as its confidence interval will be estimated.

Secondary Objectives

All secondary objectives are considered exploratory in nature, and type I error will not be controlled for multiplicity. P-values for these statistical tests will be provided for descriptive purposes. However, if a statistical test on a secondary outcome is significant at the 2-sided significance level of 0.01, the finding will be considered worthy of future investigation.

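### The primary endpoint has no time limit, yet the 80% it is tested against is a 42-day surgical exploration rate, and late or one-dose surgery has no scoring rule

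*Combined protocol and SAP*

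**What the plan says.** The primary objective in 4.1 is to "determine whether the surgery feasibility rate of neoadjuvant pembrolizumab is not significantly worse than the historical surgical feasibility rate of neoadjuvant chemotherapy". Sections 4.1 and 27.1 give the same definition of the endpoint: "Surgery feasibility rate of a neoadjuvant therapy is the percent of patients who are able to undertake surgery after the neoadjuvant therapy". It contains no time limit.

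Both sections take the null value from a cited chemotherapy trial, in which "approximately 80% of subjects undergo surgical exploration within 42 days of day 1 of the last cycle of standard neoadjuvant chemotherapy". That is a named event (exploration) with a named clock.

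The statistical analysis plan within 27.1 sets the denominator as "patients who meet eligibility criteria and has received at least 1 dose of pembrolizumab" and says that the rate and its confidence interval will be estimated. It gives no rule for the numerator beyond the definition above.

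A surgery window appears in 9.5: "Surgery to occur at 4-8 weeks (days 29-56) or subject will be removed from trial unless approved by PI". The study schedule in Appendix A counts those days from cycle 1 day 1. For patients whose drug is delayed more than two weeks by a related adverse event, 11.4 says that "pembrolizumab will be discontinued and patients should proceed to surgical resection when clinically appropriate".

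**The concern.** The test compares two different quantities. The trial counts anyone able to have surgery, at any time. The benchmark counts only those explored within 42 days of day 1 of the last cycle. The first can only equal or exceed the second in the same patients.

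The direction matters because feasibility is the null hypothesis (p at least 0.80) and is kept unless the data reject it. Each late operation counted as a success makes a true shortfall against the benchmark harder to see. The trial is open-label with 30 evaluable patients, so one or two scoring decisions, made after outcomes are known, can change the conclusion.

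The event is also loose. Being able to undertake surgery leaves open a fit patient who is never operated on, whereas the benchmark requires exploration.

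**Working it through.** **Inputs.** From 4.1 and 27.1: null rate 0.80, alternative 0.65, n = 30 evaluable, one-sided level 15%, stated power 84.6%, and a 42-day benchmark from day 1 of the last cycle. From 9.5 and Appendix A: surgery on days 29-56 from cycle 1 day 1. Dose 2 is planned for day 22; 11.3.2 adds that "Trial treatment may be administered up to 3 days before or after the scheduled Day 1 of each cycle due to administrative reasons". From 11.1 and 15.1: delays of up to 3 weeks (21 days) are mentioned.

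**Step 1: where the 42-day limit falls against the window.** Limit = day of last cycle + 42.

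| Case | Day 1 of last cycle | 42-day limit | Surgery by day 56 within 42 days? |
|---|---|---|---|
| Two doses, dose 2 on time | 22 | 64 | Always |
| Two doses, dose 2 three days early | 19 | 61 | Always |
| Two doses, dose 2 delayed 21 days | 43 | 85 | Always |
| One dose, clock from last cycle received | 1 | 43 | Only to day 43 |
| One dose, clock from planned cycle 2 | 22 | 64 | Always |

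For two-dose patients the window is therefore stricter than the benchmark. The mismatch is confined to two groups:

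- operations after day 56, approved by the PI, that also exceed 42 days from the last cycle;
- one-dose patients, if the last cycle means the last one received. Days 44-56 are then inside the window but past the limit. If it means planned cycle 2, in-window surgery is never late.

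**Step 2: the plan's own power.** A normal approximation using the null variance throughout has standard error √(0.80 × 0.20 / 30) = 0.0730. The critical proportion is 0.80 − 1.0364 × 0.0730 = 0.7243. Power = Φ((0.7243 − 0.65) / 0.0730) = 0.8455, which reproduces 84.6%.

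**Step 3: an exact cut-off.** The plan states none, so one is assumed. For X ~ Binomial(30, p):

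- P(X ≤ 21 | 0.80) = 0.1287 and P(X ≤ 22 | 0.80) = 0.2392, so 21 is the largest cut-off within 15%.
- P(X ≤ 21 | 0.65) = 0.7753. This is the starting point below. Its difference from 84.6% is a separate matter of exact against approximate calculation.

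**Step 4: effect of counting late operations.** Let T be the number explored within 42 days, T ~ Binomial(30, 0.65), and k the number of late operations counted as successes. H0 is rejected only if T + k ≤ 21, that is T ≤ 21 − k.

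| k | Probability | Chance of detecting the shortfall |
|---|---|---|
| 0 | P(T ≤ 21) = 0.7753 | 77.5% |
| 1 | P(T ≤ 20) = 0.6425 | 64.2% |
| 2 | P(T ≤ 19) = 0.4922 | 49.2% |

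Modelling late surgery as an added share gives a similar picture: P(X ≤ 21) is 65.9% at 0.65 + 0.03 and 56.8% at 0.65 + 0.05.

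**Step 5: one data set, two conclusions.** If 23 of 30 are operated on, P(X ≤ 23 | 0.80) = 0.393 and H0 stands. If two of those 23 were late and are scored as failures, the count is 21, the probability is 0.129, and H0 is rejected at 15%.

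**The case against.** **The window already handles most of this.** For two-dose patients, surgery by day 56 always satisfies 42 days. This stands, and it limits the point to exceptions. It does not close the gap, because the window's stated consequence is removal from the trial, the PI can waive it, and no text turns either outcome into a success, a failure or a non-evaluable patient. A reader might infer that the primary result as a whole is biased; the documents do not support that.

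**One-dose patients may not be affected.** A reader might infer that one-dose surgery on days 44-56 plainly breaches the benchmark. That depends on taking the last cycle as the last one received. The documents do not say so, nor how the cited trial timed patients who stopped early. With planned cycle 2 as origin the limit is day 64 and the difficulty disappears for in-window surgery. The objection stands: the documents support only that the origin is undefined.

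**The 11.4 route is not a separate exemption.** Nothing there releases patients from 9.5, so surgery after day 56 still needs PI approval to avoid removal. This also stands.

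**A 42-day clock has its own distortions.** From the last cycle received, a patient whose dose 2 is held beyond two weeks (past day 36 = 22 + 14) has about a week before day 43. From a dose 2 given on day 43, the limit is day 85, which is 29 days beyond the window. These are reasons to fix the origin in advance and report elapsed time, not to leave the endpoint untimed.

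**Error could run the other way.** If removal under 9.5 were scored as failure, unapproved surgery on days 57-64 after an on-time dose 2 would meet the benchmark yet fail here. That is possible, but a large inflation of false shortfalls would need several such patients, and no passage suggests how many to expect.

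**An untimed figure exists elsewhere.** The second safety criterion in 27.1 uses a 20% limit on patients unable to reach surgery. It covers only adverse events attributed to neoadjuvant therapy, and the documents do not show whether it comes from the trial behind 0.80. It does not supply an untimed benchmark.

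**Conclusion.** The concern holds in limited form and should be fixed. The endpoint is untimed, its null value is a 42-day exploration rate, and nothing ties the surgery window to scoring. Taken literally, the comparison leans towards finding feasibility adequate.

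Confidence is high on the missing clock and scoring rule. How one-dose patients are affected depends on a reading of the last cycle that the documents leave open.

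The size is not known. The fall from 77.5% to 64.2% or 49.2% rests on an assumed cut-off (at most 21 of 30), an assumed true 42-day rate of 65%, and one or two late operations. The plan gives neither the cut-off nor a late-surgery rate, and no untimed rate from the cited trial. If there is no late, one-dose or out-of-window surgery, nothing changes.

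**What to change.** In 4.1 and 27.1:

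- For the comparison with 0.80, define success as surgical exploration within 42 days of day 1 of the last neoadjuvant cycle.
- Keep all eligible patients with at least one dose in the denominator. Everyone without timely exploration is a failure, including those removed under 9.5.
- For one-dose patients, choose one origin in advance (last cycle received or planned cycle 2) as the main rule, and report the other as a sensitivity analysis.
- Report surgery at any time as a secondary rate.
- Report days from cycle 1 day 1 to surgery descriptively, because a clock started at a delayed dose 2 does not register that delay.

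In 9.5, add one sentence saying that neither PI approval nor removal changes endpoint status. The surgery window stays as it is.

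Separately, the passages on dose delay differ: up to 3 weeks in 11.1, discontinuation after more than two weeks in the text of 11.4, "Toxicity does not resolve within 12 weeks of last dose" in its Table 1, and a 21-day limit in 15.1. They affect who reaches surgery after one dose, and the sponsor must reconcile them; no value is proposed here.

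The cost is wording, plus dose and surgery dates. Sample size, null and alternative rates and the power calculation are unchanged. The estimated rate may be slightly less favourable than an untimed count. If the last cycle received is chosen as origin, some in-window one-dose operations will count as failures in the main analysis; the sensitivity analysis will show how many.

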11.5 Rescue Medications & Supportive Care

11.5.1 Supportive Care Guidelines

Subjects should receive appropriate supportive care measures as deemed necessary by the treating investigator. Suggested supportive care measures for the management of adverse events with potential immunologic etiology are outlined below. Where appropriate, these guidelines include the use of oral or intravenous treatment with corticosteroids as well as additional anti-inflammatory agents if symptoms do not improve with administration of corticosteroids. Note that several courses of steroid tapering may be necessary as symptoms may worsen when the steroid dose is decreased. For each disorder, attempts should be made to rule out other causes such as metastatic disease or bacterial or viral infection, which might require additional supportive care. The treatment guidelines are intended to be applied when the investigator determines the events to be related to pembrolizumab.

Note: if after the evaluation the event is determined not to be related, the investigator is instructed to follow the ECI reporting guidance (Section 20.7).

It may be necessary to perform conditional procedures such as bronchoscopy, endoscopy, or skin photography as part of evaluation of the event. Suggested conditional procedures, as appropriate, can be found in the ECI guidance document.

- **Pneumonitis:**

- For **Grade 2 events**, treat with systemic corticosteroids. When symptoms improve to Grade 1 or less, steroid taper should be started and continued over no less than 4 weeks.
- For **Grade 3-4 events**, immediately treat with intravenous steroids. Administer additional anti-inflammatory measures, as needed.
- Add prophylactic antibiotics for opportunistic infections in the case of prolonged steroid administration.

- **Diarrhea/Colitis:**

Subjects should be carefully monitored for signs and symptoms of enterocolitis (such as diarrhea, abdominal pain, blood or mucus in stool, with or without fever) and of bowel perforation (such as peritoneal signs and ileus).

- All subjects who experience diarrhea/colitis should be advised to drink liberal quantities of clear fluids. If sufficient oral fluid intake is not feasible, fluid and electrolytes should be substituted via IV infusion. For Grade 2 or higher diarrhea, consider GI consultation and endoscopy to confirm or rule out colitis.
 - For **Grade 2 diarrhea/colitis**, administer oral corticosteroids.

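### The primary endpoint has no time limit but its 80% benchmark has one; the gap is confined to late PI-approved surgery, surgery after removal from trial, and one-dose patients operated on after day 43

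*Combined protocol and SAP*

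**What the plan says.** Sections 4.1 and 27.1 define the primary endpoint in the same terms: "Surgery feasibility rate of a neoadjuvant therapy is the percent of patients who are able to undertake surgery after the neoadjuvant therapy". Neither gives a day limit. The Statistical Analysis Plan paragraph of 27.1 analyses all evaluable patients, "who are defined as the patients who meet eligibility criteria and has received at least 1 dose of pembrolizumab", and adds no timing rule.

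The null value of 0.80 comes from a published neoadjuvant chemotherapy trial, in which "approximately 80% of subjects undergo surgical exploration within 42 days of day 1 of the last cycle of standard neoadjuvant chemotherapy". The alternative is 0.65, and the one-sided level is 15%.

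Surgical timing is handled under trial conduct, not in the endpoint. Section 9.5 states: "Surgery to occur at 4-8 weeks (days 29-56) or subject will be removed from trial unless approved by PI". Section 3.2 and Appendix A count these days from the first pembrolizumab dose. Section 11.4 stops pembrolizumab when a related adverse event delays it by more than two weeks, after which "patients should proceed to surgical resection when clinically appropriate"; no day is given.

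**The concern.** The observed rate and the rate it is tested against should count the same event. Here the benchmark treats an operation after its 42-day limit as a failure, while the endpoint definition, read literally, treats it as a success.

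The direction matters. The objective is to show that the regimen is not significantly worse than chemotherapy, so failing to reject H0 is the favourable result. Counting late operations can only raise the observed rate and make rejection less likely. Some of them would come from patients held up by drug toxicity, which a feasibility endpoint is meant to detect. The second safety criterion in 27.1 (more than 20% unable to have surgery because of adverse events) does not cover this, because it has no time limit either.

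**Working it through.** **1. The plan's own power.** Inputs from 27.1: p0 = 0.80, p1 = 0.65, n = 30, one-sided alpha 0.15. The normal approximation with the null variance gives

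Φ((0.80 − 0.65)/√(0.80 × 0.20/30) − 1.036) = Φ(2.054 − 1.036) = 0.8455,

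which reproduces the stated 84.6%.

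**2. An exact rule for the illustration.** The plan gives no cut-off. For X ~ Binomial(30, 0.80), P(X ≤ 21) = 0.1287 and P(X ≤ 22) = 0.2392. The largest cut-off within 15% is therefore 21 or fewer of 30, with size 0.129. Its exact power at 0.65 is 0.7753.

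**3. Where the benchmark's limit falls.** The limit is the day of the last neoadjuvant dose plus 42.

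| Last neoadjuvant dose | Benchmark limit | Day 56 is this long after it |
|---|---|---|
| Dose 2 on time, day 22 | 22 + 42 = day 64 | 56 − 22 = 34 days |
| Dose 2 two weeks late, day 36 | 36 + 42 = day 78 | 56 − 36 = 20 days |
| Dose 2 three weeks late, day 43 | 43 + 42 = day 85 | 56 − 43 = 13 days |
| Dose 1 only, day 1 | 1 + 42 = day 43 | 56 − 1 = 55 days |

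Whenever dose 2 is given, surgery inside the 9.5 window also meets the benchmark's limit. The ±3-day visit allowance changes the 34 days to between 31 and 37, still under 42.

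**4. Where the mismatch can arise.**

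- (a) Surgery approved by the PI after day 56. Section 9.5 sets no upper limit. After an on-time dose 2, days 57-64 still meet the benchmark; later days do not.
- (b) Surgery after removal from trial. The patient remains in the analysis set (eligible, at least one dose), and no text says how the operation is scored.
- (c) Only dose 1 given and surgery after day 43, for example after the 11.4 stop. Days 44-56 are inside the 9.5 window but past the benchmark's limit, so reading 9.5 into the endpoint would not remove this case.

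**5. Size.** One patient is 1/30 = 3.3 points. The documents give no late-surgery rate, so the shares below are assumptions. Suppose 65% meet the limit (the plan's alternative) and a further share is operated on late and counted:

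| Late share (points) | Counted rate | P(X ≤ 21) |
|---|---|---|
| 0 | 0.65 | 0.775 |
| 2 | 0.67 | 0.701 |
| 5 | 0.70 | 0.569 |
| 10 | 0.75 | 0.326 |

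**The case against.** The strongest reply is that the protocol does limit surgical timing. Days 29-56 apply to everyone, and after two on-time doses this is stricter than the benchmark (34 against 42 days). That stands, and it removes the problem for patients treated on schedule. A reader might infer from the endpoint wording that the whole comparison is loose because surgery counts whenever it happens. The documents do not support that; only cases (a) to (c) remain.

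Second, the scoring of late operations is unstated rather than set. A patient removed for missing the window could be read as a failure who stays in the denominator. The follow-up items in 9.8.6 and 15.1 do not name surgery after removal, so such operations might not be recorded. This also stands. The literal definition favours success, but no sentence says so.

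Third, the toxicity route is narrower than 11.4 alone suggests. Sections 11.1, 15.1 and 16.6.4 allow a three-week delay where 11.4 stops at two. If dose 2 is then given late, the benchmark's limit moves later as well. It is tempting to argue that Grade 2 pneumonitis on day 22 must push surgery past day 43, since the "steroid taper should be started and continued over no less than 4 weeks", that is, to day 50 or later (22 + 28). But Table 1 allows pembrolizumab to restart once the event resolves to Grade 0-1, and nothing says surgery must wait for the taper. The example shows that case (c) is possible, not that it will occur.

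Fourth, the benchmark is known here only from one sentence. If few operations in that study came after 42 days, the time limit matters little. The documents cannot settle this.

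**Conclusion.** The endpoint and its benchmark do not share a time limit, and the plan does not say how operations beyond the benchmark's limit are scored. The gap is confined to late surgery approved by the PI, surgery after removal from trial, and one-dose patients operated on after day 43. Any bias runs one way, toward calling the regimen not worse than chemotherapy.

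The size is unknown and may be zero. The fall in the chance of rejection from 78% to 70%, 57% or 33% depends on assumed late shares of 2, 5 or 10 points, a within-limit rate of 65%, and rejection at 21 or fewer of 30. A reader might take these as the trial's real loss of power. They are not, because the documents give no late-surgery rate. This is a cheap improvement to the definition, not a flaw that invalidates the design.

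**What to change.** In 27.1, with the same words in 4.1, count an evaluable patient as a success only if surgery was undertaken within 42 days of the last neoadjuvant pembrolizumab dose given and before any other anti-cancer therapy. Count every other evaluable patient, including those of unknown status, as a failure, whatever their trial status. Report the days 29-56 rate and the any-time rate alongside as sensitivity results.

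The cost is two or three sentences. The rule uses dose dates, the surgery date and the start of any other therapy. For patients removed from trial, the follow-up form should ask for the surgery date explicitly. No visits, scans or patients are added, and the hypotheses and sample size do not change. After two on-time doses the limit is day 64, so no operation in the 9.5 window is lost.

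There are two downsides. A one-dose patient operated on in days 44-56 becomes a failure although inside the protocol window. A patient whose dose 2 was delayed may count as a success after day 56 (up to day 78 if it was given on day 36). The days 29-56 rate shows the effect of both. Tying success to days 29-56 alone would be simpler, but in one-dose patients it would still differ from the benchmark.

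### The stated 84.6% power is an optimistic approximation; with 30 evaluable patients the attainable power is 77.5%, and enrolment, loss rate and accrual time conflict between sections

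*Combined protocol and SAP*

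**What the plan says.** Sections 4.1 and 27.1 set up the same primary test. The null is a surgery feasibility rate of at least 0.80, taken from a historical neoadjuvant chemotherapy trial, and the alternative of interest is 0.65. The level is one-sided 15%. Section 27.1 says "With 30 evaluable patients receiving protocol treatment, the study has approximately 84.6% power rejecting" the null at 0.65, and section 4.1 repeats that "the study has approximately 84.6% power rejecting" it.

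Neither section names a test or a critical value. The Statistical Analysis Plan paragraph of 27.1 says the primary endpoint "will be analyzed using the data from all evaluable patients", meaning eligible patients with at least one dose. It promises an estimate and a confidence interval, without a confidence level or decision rule.

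On enrolment:
- Section 4.1: "Taking 5% rate of cancellation and ineligibility into account, the trial will enroll a total of 32 patients". The table in 3.1 also lists 32 subjects.
- Section 27.1, Overview: "Taking 15% rate of cancellation and ineligibility into account, the trial will enroll a total of 35 patients". Its accrual stop agrees with 35: "The trial will be stopped for accrual whenever a total of 35 patients are registered".

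On accrual time, 3.1 gives about three years. Section 27.1 says: "With an expected rate of 2 patients being enrolled each month, the trial will take about 16 months to reach the target accrual".

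Section 27.1 also has a separate feasibility criterion. The therapy is called infeasible if the cumulative percentage of treated patients "deemed unable to go to surgery due to adverse events attributed to neoadjuvant therapy exceeds 20" percent.

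**The concern.** The number of patients who reach surgery is a whole number out of 30, so only certain pairs of alpha and power are available. A power of 84.6% at a 15% level is not one of them.

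The direction matters. The objective is to show that feasibility is not clearly worse than the historical rate, so failing to reject the null is the favourable outcome. Power is therefore the protection against passing a treatment whose true surgery rate is 65%, and overstating it overstates that protection.

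The lack of a written decision rule adds to this. The analysis uses however many patients are evaluable, and the two enrolment plans do not fix that number at 30. The enrolment figures are a separate matter: sites and the ethics board cannot tell from the current text which target, loss allowance or timeline governs.

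**Working it through.** **Inputs** (sections 4.1 and 27.1): n = 30 evaluable, p0 = 0.80, p1 = 0.65, one-sided alpha = 0.15, so z = 1.0364. Rejection is in the lower tail.

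**1. Reproducing the plan's figure.** A normal approximation with the null variance under both hypotheses:

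Phi[(0.80 − 0.65)/sqrt(0.80 × 0.20/30) − 1.0364] = Phi(0.15/0.0730 − 1.0364) = 0.8455.

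This is the stated 84.6% to within rounding. With the variance that applies at 0.65 in the power term (0.65 × 0.35 = 0.2275, against 0.16):

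Phi[(0.15 − 1.0364 × 0.0730)/sqrt(0.2275/30)] = 0.803.

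So about four points are lost before discreteness is considered.

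**2. Exact binomial, n = 30.**

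| Reject if surgeries are | Alpha at 0.80 | Power at 0.65 |
|---|---|---|
| ≤20 | 0.0611 | 0.6425 |
| ≤21 | 0.1287 | 0.7753 |
| ≤22 | 0.2392 | 0.8762 |

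The largest cut-off within 15% is 21, with power 77.5%. No cut-off gives 84.6% at that level.

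**3. Does this depend on choosing an exact test?** Not at n = 30. One-sided p-values:

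| Surgeries | Score z | Wald z | Exact |
|---|---|---|---|
| 21/30 | 0.085 | 0.116 | 0.129 |
| 22/30 | 0.181 | 0.204 | 0.239 |

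All three reject at 21 and none at 22, so all have power 77.5%.

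**4. Chance of passing a true 65% rate.**
- Implied by the plan: 1 − 0.846 = 15.4%.
- Primary test alone: P(X ≥ 22) = 1 − 0.7753 = 22.5%.
- With the 20% adverse-event rule, taking 30 treated and evaluable patients and ignoring earlier stops: more than 20% of 30 means at least 7 patients. If every missed surgery is attributed to adverse events, only 24 or more surgeries pass both rules, and P(X ≥ 24) = 5.9%. If none is so attributed, the figure stays at 22.5%.

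**5. Other evaluable counts.** The largest cut-off with exact alpha at or below 15%:

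| n | Reject if | Alpha | Power |
|---|---|---|---|
| 29 | ≤20 | 10.8% | 73.5% |
| 30 | ≤21 | 12.9% | 77.5% |
| 31 | ≤21 | 7.5% | 68.9% |
| 32 | ≤22 | 9.0% | 73.2% |
| 33 | ≤23 | 10.7% | 77.0% |
| 34 | ≤24 | 12.5% | 80.4% |
| 35 | ≤25 | 14.6% | 83.5% |

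Power is not monotone in n. It dips at 31 because ≤22 of 31 has alpha 15.08%, just over the limit.

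**6. Enrolment and accrual.** 32 × 0.95 = 30.4 and 35 × 0.85 = 29.75, so each pair is roughly consistent within itself, but the pairs disagree with each other. At 2 patients a month, 32 take 16 months and 35 take 17.5. The 16 months in 27.1 therefore fits the target in 4.1 rather than the 35 in its own section, and neither is near 36 months.

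**The case against.** The 84.6% is not a slip: it reproduces from a recognisable approximation, and the plan says approximately. At n = 30 the common tests share one cut-off, so correcting the figure would not change how any 30-patient result is read. Both statements are true. But a three-digit figure that is seven points too high is not rounding, and the error is in the direction that flatters the design.

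A second argument is that the adverse-event rule may make the whole trial stricter than the primary test. The range of 5.9% to 22.5% does straddle the implied 15.4%, and the documents do not give the split of reasons that would settle it. What stands is that 22.5% describes the primary test alone. The rule does not cover progression, refusal or other reasons for missing surgery, and 27.1 itself says attribution is difficult in this design.

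A third is that the cut-offs for other counts depend on choosing an exact test. This also stands. At 31 patients the score and Wald tests both reject at ≤22 (power 81.1%, exact alpha 15.08%). At 32 the score test rejects at ≤23 (power 84.2%, exact alpha 17.5%). That is a reason to name the test in advance, since the same data could otherwise be read either way.

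Finally, the study schema calls this a 30 patient trial. That can be read as the 30 evaluable patients, so it is not counted as a further conflict.

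**Conclusion.** The concern holds. With 30 evaluable patients at one-sided 15%, attainable power at a true rate of 65% is 77.5% (cut-off 21 of 30, alpha 12.9%), about 7 points below the stated figure. The primary test's chance of passing a 65% rate is 22.5% rather than 15.4%. Allowing for the adverse-event rule, the range is 5.9% to 22.5%, assuming all 30 are treated and evaluable and ignoring earlier stops. The figures rest on the plan's own n, rates and level, and on a non-randomised test.

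The plan also lacks a cut-off and a rule for evaluable counts other than 30. The enrolment conflict is literal in current text: 32 against 35 patients, 5% against 15% loss, and about 36 against 16 months of accrual, a gap of about 20 months. This should be fixed, but it does not undermine the design.

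**What to change.** In 4.1 and 27.1, replace the power sentence with wording such as:

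> Exact one-sided binomial test; with 30 evaluable patients H0 is rejected if 21 or fewer undergo surgery; exact alpha 12.9%, exact power 77.5% at p = 0.65.

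In the analysis paragraph of 27.1, add:

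> For any other evaluable count, the cut-off is the largest with exact alpha at or below 15% at p = 0.80.

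Attach the cut-offs for 29 to 35 patients tabulated above, with a note that power is not monotone in n and falls to 68.9% at 31.

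Separately, choose one loss rate, one enrolment target and one accrual time, and use them in 3.1, 4.1, 27.1 and the accrual stop.

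The cost is wording in three sections and a less favourable stated power. Fixing an exact rule also means accepting lower power at some counts than a z-test would give, in return for keeping alpha within the stated 15%. The correction itself needs no added patients. If the sponsor wants power close to the stated figure, 35 evaluable (not merely registered) patients would give 83.5%; that choice belongs with the decision on the enrolment target.
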